	Screening Period with Obinutuzumab Pre-treatment				Cycle 1
Day	Day -28 to Day -8	Day -7	Day -6	Day -5 to Day -1	Day 1
Assessments					See relevant SoA depending on applicable schedule for ongoing assessments
Informed Consent^a	x				
Eligibility	x				
Demography	x				
Medical History	x				
Pulmonary Function Tests^b	x				
Archival Tissue^c	x				
Previous and Concomitant Treatments	x	x	x	x	
Adverse Events	x	x	x	x	
Physical Examination	x	x	x		
Anthropometric Measurements^d	x				
Vital Signs^e	x	x	x	x	
ECOG Performance Status	x			x	
ECG-12 lead^f	x			x	
Pregnancy Tests^g	x			x	
Hematology^h	x	x		x	
Blood Chemistry^h	x	x		x	
Coagulation^h	x	x		x	

Table 6 Screening Schedule of Assessments with Obinutuzumab Pretreatment (cont.)

	Screening Period with Obinutuzumab Pre-treatment				Cycle 1
Day	Day -28 to Day -8	Day -7	Day -6	Day -5 to Day -1	Day 1
Assessments					See relevant SoA depending on applicable schedule for ongoing assessments
Serology ⁱ	x				
Urinalysis ^h	x				
Fresh Tumor Biopsy ^j	x ^j				
Tumor Assessment ^k	x				
Tumor Kinetics ^l	x				
Administration of obinutuzumab ^m		x	x		
Obinutuzumab PK Sample		x ⁿ	x ^p		
ADA to Obinutuzumab		x ⁿ			
sCEA	x ^o				
PD Blood Flow Cytometry		x ⁿ			
PD Blood Cytokines		x ⁿ			

ADA = anti-drug antibody; AE = adverse event; C = Cycle; CEA = carcinoembryonic antigen; ct = circulating tumor; D = day; *discont* = discontinuation; DNA = deoxyribonucleic acid; ECG = electrocardiogram; ECOG = Eastern Cooperative Oncology Group; G2 = grade 2; HIV = human immunodeficiency virus; IgE = immunoglobulin E; *incl* = including; IRR = infusion related reaction; PD = pharmacodynamics; PK = pharmacokinetic; RBR = Research Biosample Repository; RECIST = Response Evaluation Criteria in Solid Tumors; RNA = ribonucleic acid; sCEA = soluble CEA; TCR = T cell receptor.

Table 6 Screening Schedule of Assessments with Obinutuzumab Pretreatment (cont.)

- a Informed consent must be obtained before any study-specific procedures and may be obtained > 28 days before the start of study treatment..*
- b Pulmonary function tests should include spirometry; forced expiratory volume (FEV1), forced vital capacity (FVC) and Diffusion capacity (DLCO).*
- c As part of the eligibility procedure, CEA expression will be confirmed on archival tumor material, with the exception of CRC participants. If no archival tumor sample is available, fresh sample will be collected and be assessed (the same sample would constitute as baseline screening sample if participant is enrolled). Archival tissue should be submitted for additional biomarker assessments for all participants (if available).*
- d Weight to be recorded pre-infusion. Height to be measured at screening only.*
- e Vital signs include systolic and diastolic blood pressure; pulse rate; temperature; respiratory rate and oxygen saturation.*
- f 12-lead ECG at screening (within one week before obinutuzumab pre-treatment and within 5 days of the first dose of RO7172508). Additional unscheduled ECG assessments in triplicate should be performed in case of abnormalities and if clinical symptoms occur. Recording must be done prior to PK sampling.*
- g Serum pregnancy test at screening, within 7 days prior to first dose of obinutuzumab. Results must be obtained and reviewed prior to administration of obinutuzumab. Prior to the first dose of RO7172508 a urine pregnancy test will be performed. If a urine pregnancy test is positive, it must be confirmed by a blood pregnancy test.*
- h Hematology, blood chemistry, coagulation, and urinalysis can be performed within 24 hours (up to 72 hours if during weekend) prior to scheduled dosing. Screening results can be within 1 week prior to C1D1 but after obinutuzumab pre-treatment. Results must be obtained and reviewed prior to administration of RO7172508 or obinutuzumab.*
- i Serology (as per local regulations) includes HIV, hepatitis B surface antigen, total hepatitis B core antibody, hepatitis C virus antibody. Results must be obtained and reviewed prior to administration of obinutuzumab.*
- j Tumor biopsy samples will be collected during screening. If a fresh biopsy is performed for screening purposes, this can be used as the baseline sample. This biopsy should be taken BEFORE obinutuzumab is administered.*
- k Tumor response is assessed by the Investigator per RECIST V1.1 with the use of physical examination and image-based evaluation. All measurable and evaluable lesions should be assessed and documented during the screening period before obinutuzumab pre-treatment.*
- l To allow estimation of tumor growth rate before start of treatment an exploratory assessment of tumor kinetics will be made by comparing post treatment scans with at least 2 pre-treatment scans not older than 12 weeks prior to C1D1 if available. One of the pre-treatment scans will be the study baseline scan taken during screening and the second will be within the preceding 12 weeks.*
- m Obinutuzumab to be administered either on Day-7 (2000 mg) or on Day-7 and Day-6 (1000 mg each day). If obinutuzumab is given only on one day, then the schedule for Day-7 should be followed including an end of infusion sample.*
- n Samples should be taken BEFORE obinutuzumab is administered.*
- o sCEA to be assessed for enrollment in cohorts with RO7172508 doses < 12 mg.*
- p Sample to be taken end of infusion only*

Table 7 Schedule of Assessments Part II: Multiple Participant Cohorts SC Q3W

Cycle (21 days)	Screening ^x	Cycle 1 - 2						Cycle 3 - 4 ^a				Cycle 5 onwards ^a			End of Treatment	Safety Follow-Up	Survival Follow-Up ^q	Unscheduled (Safety)	
Day	D-28 to D-1	Day 1	Day 2	Day 3	Day 5	Day 8	Day 15	Day 1	Day 3 ^p	Day 8	Day 15	Day 1	Day 3 ^{c, p}	Day 15					
Assessments ^a		pre-dose	24 hrs +/- 2 hrs	48 hrs +/- 4 hrs	+/- 1 day			pre-dose	48 hrs +/- 1 day			pre-dose	48hrs +/- 4 hrs		incl. early discont. visit (e.g. progressive disease)	60 Days after last treatment (+/- 5 Days)	90 Days after last treatment then every 3 mths ^q	e.g. In the event of an IRR ≥G2 ^o	
Informed Consent ^b	x																		
Eligibility	x																		
Demography	x																		
Medical History	x																		
Pulmonary Function Tests ^w	x																		
Archival Tissue ^h	x																		
Previous and Concomitant Treatments	x	x	x	x	x	x	x	x	x	x	x	x	x	x	x	x	x	x	x
Adverse Events	x	x	x	x	x	x	x	x	x	x	x	x	x	x	x	x	x	x	x
Physical Examination	x	x						x				x			x	x			x
Anthropometric Measurements ^s	x	x						x				x			x	x			x
Vital Signs ^v	x	x	x	x	x	x	x	x	x	x	x	x	x	x	x	x			x

Table 7 Schedule of Assessments Part II: Multiple Participant Cohorts SC Q3W (cont.)

Cycle (21 days)	Screening ^x	Cycle 1 - 2						Cycle 3 - 4 ^a				Cycle 5 onwards ^a			End of Treatment	Safety Follow-Up	Survival Follow-Up ^q	Unscheduled (Safety)
Day	D-28 to D-1	Day 1	Day 2	Day 3	Day 5	Day 8	Day 15	Day 1	Day 3 ^p	Day 8	Day 15	Day 1	Day 3 ^{c, p}	Day 15				
Assessments ^a		pre-dose	24 hrs +/- 2 hrs	48 hrs +/- 4 hrs	+/- 1 day			pre-dose	48 hrs +/- 1 day			pre-dose	48hrs +/- 4 hrs		incl. early discont. visit (e.g. progressive disease)	60 Days after last treatment (+/- 5 Days)	90 Days after last treatment then every 3 mths ^q	e.g. In the event of an IRR ≥G2 ^o
ECOG Performance Status	x	x						x				x			x	x		
ECG-12 lead ^d	x	x						x				x ^d				x		
Pregnancy Test ^e	x							x				x				x		
Hematology ^f	x	x	x	x	x	x	x	x	x	x	x	x	x	x	x	x		x
Blood Chemistry ^f	x	x	x	x	x	x	x	x	x	x	x	x	x	x	x	x		x
Coagulation ^f	x	x	x	x	x	x	x	x	x	x	x	x	x	x	x	x		x
Serology ^r	x																	
Urinalysis ^f	x	x						x				x			x	x		
Fresh Tumor Biopsy ^g	x ^g					x ^g									x ^g			
Tumor Assessment ⁱ	x							x ⁱ				x ⁱ			x			
Tumor Kinetics ^l	x																	
Administration of obinutuzumab ^x	x ^x																	

Table 7 Schedule of Assessments Part II: Multiple Participant Cohorts SC Q3W (cont.)

Cycle (21 days)	Screening ^x	Cycle 1 - 2						Cycle 3 - 4 ^a				Cycle 5 onwards ^a			End of Treatment	Safety Follow-Up	Survival Follow-Up ^q	Unscheduled (Safety)
Day	D-28 to D-1	Day 1	Day 2	Day 3	Day 5	Day 8	Day 15	Day 1	Day 3 ^p	Day 8	Day 15	Day 1	Day 3 ^{c, p}	Day 15				
Assessments ^a		pre-dose	24 hrs +/- 2 hrs	48 hrs +/- 4 hrs	+/- 1 day			pre-dose	48 hrs +/- 1 day			pre-dose	48hrs +/- 4 hrs		incl. early discount. visit (e.g. progressive disease)	60 Days after last treatment (+/- 5 Days)	90 Days after last treatment then every 3 mths ^q	e.g. In the event of an IRR ≥G2 ^o
Obinutuzumab PK Sample ^x	x ^x	x				x ^u		x				x ^y			x			
ADA to obinutuzumab ^x	x ^x											x ^y						
Administration of RO7172508 ^j		x ^j						x ^j				x ^j						
RO7172508 PK Sample		x	x	x	x	x	x	x	x	x	x	x	x	x	x	x		x
ADA to RO7172508		x			x	x	x	x		x	x	x			x	x		x
sCEA	x	x ^z	x	x	x	x	x	x	x	x	x	x	x		x	x		x
PD Blood Flow Cytometry		x	x			x		x		x		x ^{aa}			x			
PD Blood Cytokines		x	x	x	x	x	x		x	x		x ^m	x ^m		x			x ^o
TCR Vβ ^k		x ^k										x ^k						
CtDNA/tumor markers		x ^k						x				x ⁿ						
Clinical Genotyping		x ^u																
RBR Sample (DNA)		x ^u																

Table 7 Schedule of Assessments Part II: Multiple Participant Cohorts SC Q3W (cont.)

Cycle (21 days)	Screening ^x	Cycle 1 - 2						Cycle 3 - 4 ^a				Cycle 5 onwards ^a			End of Treatment	Safety Follow-Up	Survival Follow-Up ^q	Unscheduled (Safety)	
Day	D-28 to D-1	Day 1	Day 2	Day 3	Day 5	Day 8	Day 15	Day 1	Day 3 ^p	Day 8	Day 15	Day 1	Day 3 ^{c, p}	Day 15					
Assessments ^a		pre-dose	24 hrs +/- 2 hrs	48 hrs +/- 4 hrs	+/- 1 day			pre-dose	48 hrs +/- 1 day			pre-dose	48hrs +/- 4 hrs		incl. early discont. visit (e.g. progressive disease)	60 Days after last treatment (+/- 5 Days)	90 Days after last treatment then every 3 mths ^q	e.g. In the event of an IRR ≥G2 ^o	
RBR Sample (RNA)		x ^u										x ⁿ							
IgE & Tryptase																			x ^o

ADA = anti-drug antibody; AE = adverse event; C = Cycle; CEA = carcinoembryonic antigen; ct = circulating tumor; D = day; discont = discontinuation; DNA = deoxyribonucleic acid; ECG = electrocardiogram; ECOG = Eastern Cooperative Oncology Group; G2 = grade 2; HIV = human immunodeficiency virus; IgE = immunoglobulin E; incl = including; IRR = infusion related reaction; PD = pharmacodynamics; PK = pharmacokinetic; RBR = Research Biosample Repository; RECIST = Response Evaluation Criteria in Solid Tumors; RNA = ribonucleic acid; sCEA = soluble CEA; TCR = T cell receptor.

- a All visits from Cycle 3 onwards should occur within a 3-day time window, unless otherwise indicated and all assessments or samples where indicated should be taken prior to the administration of RO7172508.
- b Informed consent must be obtained before any study-specific procedures and can be obtained > 28 days from the start of screening.
- c Visit to be done only every second cycle after Cycle 5. (i.e. C7, C9 etc.).
- d 12-lead ECG at screening (within one week before first dose of RO7172508). After Cycle 4, 12-lead ECG to be done only at every second cycle (i.e. Cycle 6, Cycle 8 etc.). Additional unscheduled ECG assessments in triplicate should be performed in case of abnormalities and if clinical symptoms occur. Recording must be done prior to PK sampling.
- e Serum pregnancy test at screening, within 7 days prior to first dose, and at the safety follow-up visit; a urine pregnancy test will be performed at specified subsequent visits. If a urine pregnancy test is positive, it must be confirmed by a blood pregnancy test. Results must be obtained and reviewed prior to administration of RO7172508.
- f Hematology, blood chemistry, coagulation, and urinalysis can be performed within 24 hours (up to 72 hours if during weekend) prior to scheduled dosing. Screening results can be within 1 week prior to C1D1. Results must be obtained and reviewed prior to administration of RO7172508.

Table 7 Schedule of Assessments Part II: Multiple Participant Cohorts SC Q3W (cont.)

g	Tumor biopsy samples will be collected during screening, once during the study treatment period at Cycle 2 Day 8 and optionally at the end of treatment visit ONLY if the reason for discontinuation is progressive disease. If a fresh biopsy is performed for screening purposes, this can be used as the baseline sample.
h	As part of the eligibility procedure, CEA expression will be confirmed on archival tumor material, with the exception of CRC participants. If no archival tumor sample is available, fresh sample will be collected and be assessed (the same sample would constitute as baseline screening sample if participant is enrolled). Archival tissue should be submitted for additional biomarker assessments for all participants (if available).
i	Tumor response is assessed by the Investigator per RECIST V1.1 with the use of physical examination and image-based evaluation. All measurable and evaluable lesions should be assessed and documented during the screening period, within 7 days before Cycle 3 Day 1, thereafter every 6 weeks (\pm 7 days) for 12 weeks, and then every 12 weeks (\pm 7 days) until disease progression or death. (i.e. screening, C3, C5, C7, C11, C15, C19 etc.).
j	All planned assessments are to be performed before administration of RO7172508. At least 24 hours (overnight) hospital stay required following administration of study drug at Cycle 1 Day 1.
k	TCR Vβ and CtDNA/tumor marker samples to be drawn at Cycle 1 Day 1 predose (baseline) and Cycle 5 Day 1 predose.
l	To allow estimation of tumor growth rate before start of treatment, an exploratory assessment of tumor kinetics will be made by comparing post-treatment scans with at least 2 pretreatment scans not older than 12 weeks prior to C1D1, if available. One of the pretreatment scans will be the study baseline scan taken during screening and the second will be within the preceding 12 weeks.
m	Cytokines from Cycle 5 onwards, samples to be taken every second cycle up to Cycle 15 (e.g. C5, C7 etc.).
n	RBR (RNA) and CtDNA/tumor markers samples to be taken on Cycle 5 only.
o	Sample to be taken only if \geq Grade 2 the safety event is suspected to be immune-related (e.g., IRR). Refer to Table 5 for additional assessments if safety event is an IRR/CRS (\geq Grade 3) that requires tocilizumab treatment. Any biopsy samples or results done as part of standard of care can be shared with the Sponsor if applicable.
p	The Day 3 visit may be adjusted +/- 1 day depending on safety and PD data. The visit optimal timepoint will be communicated to the Investigators for consistency and should occur \pm 4 hrs from each complete day of administration (i.e. 24hrs \pm 4hrs; 48 hrs \pm 4hrs; OR 72hrs \pm 4hrs).
q	Survival follow-up visit to be performed 90 days (\pm 7 Days) after the last treatment either in person or a phone call to document any ongoing or resolved AEs, and every 3 months (\pm 2 weeks) thereafter for overall survival.
r	Serology (as per local regulations) includes HIV, hepatitis B surface antigen, total hepatitis B core antibody, hepatitis C virus antibody. Results must be obtained and reviewed prior to administration of RO7172508.
s	Weight to be recorded pre-infusion. Height to be measured at screening only.
t	Required for Cycle 5 only.
u	Samples to be collected only in Cycle 1
v	Vital signs include systolic and diastolic blood pressure; pulse rate; temperature; respiratory rate and oxygen saturation.
w	Pulmonary function tests should include spirometry; forced expiratory volume (FEV1), forced vital capacity (FVC) and Diffusion capacity (DLCO).

Table 7 Schedule of Assessments Part II: Multiple Participant Cohorts SC Q3W (cont.)

x	Refer to Table 6 in the event obinutuzumab pre-treatment is implemented for specific additional assessments during the screening period.
y	Obinutuzumab ADA and PK samples to be taken only in Cycle , 5 and 7 before administration of RO7172508.
z	sCEA to be assessed for enrollment in cohorts with RO7172508 doses < 12 mg.
aa	PD blood flow cytometry to be taken from Cycle 5 onwards only at Cycles 8,12 and 16 at predose

2. **INTRODUCTION**

2.1 **STUDY RATIONALE**

RO7172508 is a novel T-cell bispecific (TCB) antibody that targets carcinoembryonic antigen (CEA) expressed on tumor cells and cluster of differentiation 3 (CD3) epsilon chain (CD3e) present on T-cells.

Despite great progress in recent years, management of patients with many types of advanced solid tumors remains highly challenging. There has been renewed interest over the last few years in engaging the immune system to fight cancer. One approach currently in development is to activate T-cells against the tumor by using TCBs. The Sponsor has developed a novel TCB (RO7172508) that targets human CEA on tumor cells and CD3 on T-cells, which results in selective T-cell-mediated killing of cancerous CEA-expressing cells. CEA-related cell adhesion molecule 5 (CEACAM5) or CD66e, is a protein with molecular weight of 180–200 kDa that belongs to the CEACAM superfamily. High expression of CEA is found in various tumor types ([Thompson et al 1991](#)), including colorectal cancer, pancreatic cancer, gastric cancer, non-small cell lung cancer (NSCLC), head and neck cancer, and breast cancer among others, whereas low expression of CEA was found in small-cell lung cancer and glioblastoma ([RO7172508 Investigator's Brochure](#)). RO7172508 will be used in indications where significant subsets of patients have tumors expressing CEA.

The clinical proof-of-concept was demonstrated with *cibisatamab* (RO6958688, CEA-TCB), a TCB antibody targeting CEA currently in clinical development, which induced objective radiological responses both as a single agent and in combination with a programmed death-ligand 1 (PD-L1) checkpoint inhibitor atezolizumab with an acceptable safety profile (Study BP29541 [NCT02324257], Study WP29945 [NCT02650713]). RO7172508 differentiates from *cibisatamab* by having a different binding CEA domain with increased affinity to CEA exhibiting tumor cell lysis in cells with lower CEA expression level and a prolonged half-life. RO7172508 is therefore expected to show enhanced anti-tumor activity, resulting in an increased response rate in high-CEA-expressing tumors when compared to *cibisatamab*, and enabling treatment of low-CEA-expressing tumors which are not targeted by *cibisatamab*.

The aim of the current study is to define the safety profile of RO7172508 when used as a single agent, generate pharmacokinetic (PK), pharmacodynamics (PD), and efficacy data that will allow selection of an optimal route of administration and schedule for further development.

The development of anti-drug antibodies (ADAs) can result in a partial or complete loss of exposure and is thought to be mainly mediated by the stimulation of B-cells, which leads to generation of antibody-producing plasma cells. The use of obinutuzumab as a pre-treatment (if needed) to inhibit or attenuate ADA responses by depletion of B-cells has been implemented in this study and is supported by nonclinical and clinical studies further described in Section 2.2.2. For the benefit/risk assessment of obinutuzumab pre-treatment, please refer to Section 2.3.

The rationale for the study design is provided in Section 4.2.

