- 12-lead ECG at screening (within one week before first dose of RO7172508). After Cycle 4, 12-lead ECG to be done only at every second cycle (i.e. Cycle 6, Cycle 8 etc.). Additional unscheduled ECG assessments in triplicate should be performed in case of abnormalities and if clinical symptoms occur. Recording must be done prior to PK sampling.

Table 2 Part II: Multiple Participant Cohorts IV Q3W/Multiple Ascending Dose-Escalation (cont.)

- e) Serum pregnancy test at screening, within 7 days prior to first dose, and at the safety follow-up visit; a urine pregnancy test will be performed at specified subsequent visits. If a urine pregnancy test is positive, it must be confirmed by a blood pregnancy test. Results must be obtained and reviewed prior to administration of RO7172508.
- f) Hematology, blood chemistry, coagulation, and urinalysis can be performed within 24 hours (up to 72 hours if during weekend) prior to scheduled dosing. Screening results can be within 1 week prior to C1D1. Results must be obtained and reviewed prior to administration of RO7172508.
- g) Tumor biopsy samples will be collected during screening, once during the study treatment period at Cycle 2 Day 8 and optionally at the end of treatment visit ONLY if the reason for discontinuation is progressive disease. If a fresh biopsy is performed for screening purposes, this can be used as the baseline sample.
- h) As part of the eligibility procedure, CEA expression will be confirmed on archival tumor material, *with the exception of CRC participants*. If no archival tumor sample is available, fresh sample will be collected and be assessed (the same sample would constitute as baseline screening sample if participant is enrolled). Archival tissue should be submitted for additional biomarker assessments for all participants (if available).
- i) Tumor response is assessed by the Investigator per RECIST V1.1 with the use of physical examination and image-based evaluation. All measurable and evaluable lesions should be assessed and documented during the screening period, within 7 days before Cycle 3 Day 1, thereafter every 6 weeks (± 7 days) for 12 weeks, and then every 12 weeks (± 7 days) until disease progression or death. (i.e. screening, C3, C5, C7, C11, C15, C19 etc.).
- j) All planned assessments are to be performed before administration of RO7172508. At least 24 hours (overnight) hospital stay required following administration of study drug at Cycle 1 Day 1.

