6.6 DOSAGE MODIFICATION

In the event a dose-reduction is necessary, any subsequent study treatment will be administered after agreement with the Sponsor.

Should a participant experience a DLT in the first or in subsequent cycles or experience a toxicity of the same nature at the same or higher grade following re-exposure to RO7172508, the Investigator, after discussion with the Sponsor, will have the option to reduce the dose of RO7172508, if deemed clinically beneficial.

A delay of RO7172508 administration for up to two cycles independent of the schedule, will be acceptable to allow for resolution of toxicity to NCI CTCAE Grade ≤ 2 for hematological toxicities or Grade ≤ 1 for non-hematological toxicities (with the exception of a toxicity considered as non-RO7172508-related).

If the toxicity does not resolve to NCI CTCAE Grade ≤ 2 for hematological toxicities or ≤ 1 for non-hematological toxicities and the participant is unable to resume treatment with RO7172508 after this time (omission of two doses), no additional doses will be administered and the participant will be withdrawn from study treatment, unless the participant exhibits a clinical benefit and this is agreed by the Investigator and the Medical Monitor. It should be noted that infusions/cycles not occurring at the anticipated schedule, are considered as delayed, not missed.

Further dose-reductions may be implemented once safety and toxicity data from the dose-escalation have been evaluated.

If a participant experiences obinutuzumab-related toxicity on Day -7 that requires the subsequent administration of obinutuzumab on Day -6 to be delayed, administration of obinutuzumab up to Day -5 is acceptable. Any obinutuzumab-related toxicity should resolve to NCI CTCAE Grade ≤ 2 for hematological toxicities or ≤ 1 for non-hematological toxicities before RO7172508 administration. The first RO7172508 administration can be delayed for up to 1 week and if toxicity persists, the start of RO7172508 treatment will need to be agreed with the Medical Monitor.

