8.1 EFFICACY ASSESSMENTS

8.1.1 Tumor and Response Evaluations

Tumor assessments will be performed at the time-points defined in the SoA (Section 1.3). Tumor response will be evaluated according to RECIST v1.1 ([Appendix 6](#)) using unidimensional measurement such as CT scan or magnetic resonance imaging (MRI). Assessment of CT/MRI scans as tumor assessments will be performed at the sites during the whole study.

The data collected for RECIST v1.1 ([Appendix 6](#)) will be used by the Sponsor to calculate programmatically time-point responses for iRECIST ([Appendix 7](#)), a recently published set of guidelines developed by the RECIST working group in an effort to harmonize immune-based response criteria across the academic and industrial cancer immunotherapy field ([Seymour et al 2017](#)).

Tumor assessment will be performed according to the SoA until disease progression or death. All tumor assessments after baseline may be done within one week of the scheduled visit.

Confirmation of PRs and complete responses (CRs) will be done at the next scheduled visit after at least 28 days from the initial response.

The criteria are needed for continuing treatment beyond RECIST v1.1-defined progression as defined in Section 7.1.

Submission of the latest pre-study or historical CT scans is required for assessment of tumor kinetic modelling within 12 weeks of participant entering the study if available.

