9.4.2 Efficacy Analyses

The primary and secondary efficacy analyses will include all participants in the efficacy population with participants grouped according to cohort (and schedule if applicable) within each study part. Primary, secondary, and exploratory endpoints are described in Section 3.

The efficacy endpoints of ORR, DCR and PFS according to RECIST v1.1 will be evaluated using the methods described in [Table 22](#):

- Objective response is defined as a CR or PR, as determined by the Investigator's assessment using RECIST v1.1 and confirmed by repeat assessments ≥ 4 weeks after initial documentation. To classify a response as SD, measurements will have to be classified as stable (according to RECIST v1.1) at least once after study entry at a minimum of 6 weeks after study entry.
- ORR and DCR are both determined as the rate of participants with an observed tumor response of CR or PR (ORR) or CR, PR or SD (DCR). ORR and DCR will be derived for RECIST v1.1.
- Among participants with an objective response (responders), DOR will be defined as the time from first occurrence of a documented objective response until the time of documented disease progression or death within 30 days from last study treatment from any cause during treatment, whichever occurs first. Censoring methods will be

the same as the one applied for PFS (on-study drug treatment). This will be calculated for participants who have a best overall response of CR or PR as defined per RECIST v1.1 and per iRECIST.

- PFS (on-treatment) will be defined as the time from study treatment initiation (Cycle 1 Day 1) to the first occurrence of documented disease progression or death from any cause during treatment (death within 30 days from last study treatment), whichever occurs first. For participants who do not have documented progressive disease or death during the study, PFS will be censored at the day of the last tumor assessment. If no post study drug treatment tumor assessment is available, PFS will be censored at the day of the first study drug administration + 1 day.
- OS is defined as the time from the first dose of study treatment to the time of death from any cause on study. Participants who are still alive at the time of analysis will be censored at the time of their last study assessment (for active participants) or at the last date known alive (for participants in follow-up).

Table 22 Efficacy Statistical Analysis Methods

Endpoint	Statistical Analysis Methods

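### The first on-study scan is tied to Cycle 3 Day 1, which moves with early dosing delays while the PFS clock does not; this may distort descriptive PFS across dose cohorts, chiefly at early landmarks

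*Combined protocol and SAP*

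**What the plan says.** **First scan.** Section 1.3 (Table 1 footnote k; footnote i of Tables 2, 3, 4 and 7) says that measurable and evaluable lesions "should be assessed and documented during the screening period, within 7 days before Cycle 3 Day 1, thereafter every 6 weeks" for 12 weeks, then every 12 weeks, each ±7 days. The same footnote restates the timetable by cycle: "i.e. screening, C3, C5, C7, C11, C15, C19 etc". Section 8.1.1 ties the window to the visit: "All tumor assessments after baseline may be done within one week of the scheduled visit".

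**Delays.** Section 6.6 states: "A delay of RO7172508 administration for up to two cycles independent of the schedule, will be acceptable", so that toxicity can resolve. It adds that "infusions/cycles not occurring at the anticipated schedule, are considered as delayed, not missed".

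**PFS clock.** Section 9.4.2 defines on-treatment PFS as "the time from study treatment initiation (Cycle 1 Day 1) to the first occurrence of documented disease progression" or on-treatment death. Table 22 plans descriptive summaries by cohort and schedule, with no hypothesis test.

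**Unscheduled imaging.** Section 8.1.1.1 lets the investigator repeat CT at any time if progression is suspected, and also makes a full radiographic assessment mandatory in that case. The schedules include a tumor assessment at the end-of-treatment visit.

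No passage says that scans stay on calendar time when dosing is late, and no sensitivity analysis is planned for off-schedule scans.

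**The concern.** Silent progression is dated to the scan that finds it. If the scan moves with dosing but the clock does not, a participant held in Cycle 1 or 2 is first examined later than one dosed on time, for a reason unrelated to the tumor. Cohorts that differ in how often participants are held would then be scanned on different timetables, and their PFS summaries would not be like for like. Section 4.1.2.2 lists clinical activity among the inputs to the choice of the optimal biological dose, so a difference produced by scan timing could be read as a difference in activity.

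The second weakness is in the wording. Sites are given two timetables for later scans and are not told which governs after a delay.

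**Working it through.** **1. The plan's own timetable.** Cycles last 21 days, so cycle c starts at week 3(c − 1). C3, C5, C7, C11, C15 and C19 fall at weeks 6, 12, 18, 30, 42 and 54. The text rule (week 6, every 6 weeks for 12 weeks, then every 12 weeks) gives the same weeks. The two agree when nothing is late.

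**2. Delay before Cycle 3.** On time, Cycle 3 Day 1 is 42 days after Cycle 1 Day 1, and the 7-day window before it covers days 35 to 41. A two-cycle delay adds 2 × 21 = 42 days, giving days 77 to 83, or nominally week 12. Under either timetable the later scans move too.

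**3. Delay after the first scan.** Suppose a 3-week hold falls between Cycles 3 and 5. The calendar rule puts the second scan at week 12; the cycle list puts it at week 15.

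**4. Mean recorded PFS for a held participant.** Assumptions, not in the documents: exponential time to progression, true median m of 6, 8 or 12 weeks, no unscheduled detection. With S(t) = 0.5^(t/m), first scan at week f, and later scans at f + 6, f + 12 and every 12 weeks after that:

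mean = f + 6·S(f) + 6·S(f+6) + 12·S(f+12) / (1 − S(12))

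For m = 6:
- On time (f = 6): 6 + 3 + 1.5 + 2 = 12.50.
- Held 6 weeks (f = 12): 12 + 1.5 + 0.75 + 1 = 15.25, a rise of 2.75.

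| True median (weeks) | On time | Held 3 weeks | Held 6 weeks |
|---|---|---|---|
| 6 | 12.50 | 13.60 (+1.10) | 15.25 (+2.75) |
| 8 | 15.59 | 16.40 (+0.80) | 17.70 (+2.11) |
| 12 | 21.73 | 22.23 (+0.50) | 23.12 (+1.39) |

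**5. Direction for individuals and medians.** With a 3-week hold the scans fall at weeks 9, 15 and 21 instead of 6, 12 and 18. Progression between weeks 6 and 9 is then found at week 9 instead of week 12, which is earlier. In simulation, 27% to 30% of participants held 3 weeks are recorded earlier, and 8% to 21% of those held 6 weeks. Medians also move both ways. At a true median of 9 weeks, S(6) = 0.63 and S(12) = 0.40, so the on-time recorded median is 12. A 2-week hold gives 14, because S(8) = 0.54 is still above one half. A 4-week hold gives 10, because S(10) = 0.46.

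**6. Between cohorts.** Assume 10% held in one cohort and 40% in another. The mean shift is 0.30 times the rise in step 4:
- 3-week holds: 0.15 to 0.33 weeks.
- 6-week holds: 0.42 to 0.82 weeks.

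If 60% of progressions are caught by unscheduled imaging, multiply by 0.4; the 6-week figures become 0.17 to 0.33 weeks. The standard error of mean recorded PFS in a cohort of 6 is 3.9 weeks at a true median of 6 and 7.5 weeks at 12.

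**7. Week-8 PFS rate.** Take a true median of 9 weeks and 6-week holds. On-time participants show S(6) = 63%. Held participants show 100%, since none has been scanned.
- 10% held: 0.9 × 0.63 + 0.1 = 67%.
- 40% held: 0.6 × 0.63 + 0.4 = 78%.

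With 60% unscheduled detection the rates are 59% and 64%. True PFS is identical in both cohorts.

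**The case against.** A reader might infer that every toxicity delay postpones recorded progression and that PFS is therefore biased by dose. The documents do not support that reading, for these reasons:

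- Only delays before Cycle 3 Day 1 certainly move a scan. After that, the text rule is on calendar time and the cycle list may be no more than a gloss.
- Section 8.1.1.1 requires full imaging when progression is suspected, and stopping treatment triggers an assessment. Only silent progression during a hold is exposed.
- The documents give no delay rate by dose. Failure to recover from related toxicity that delays dosing by more than 14 days is itself a DLT (Section 4.1.3.1). The design limits DLTs: their mean proportion in the Appendix 8 simulations is 7.3% to 18.1%. Some severe toxicities lead to discontinuation instead of a hold (Section 7.1).
- PFS is secondary and descriptive, and is not named in the rule for the optimal biological dose. Section 9.4 does not expect efficacy to be a key criterion for choosing the route. Part I has one participant per cohort.

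All of this stands, and it limits the size and certainty of the point. It does not remove the mechanism: a hold in Cycles 1 to 2 moves the first scan, the clock stays fixed, imaging on suspicion does not reach silent progression, and the footnote does not settle which timetable governs later scans.

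**Conclusion.** The point holds in a limited form. The first scan is anchored to dosing, PFS is not, and the footnote's two timetables disagree once a later cycle is late. If holds become more frequent with dose, cohorts are scanned on different timetables and descriptive PFS may be distorted. The distortion is mainly in early landmark rates: 67% against 78% at week 8 in the example with 6-week holds, or 59% against 64% with substantial unscheduled detection. The between-cohort shift in the mean is under 1 week in the scenarios run, small beside the sampling error of a cohort of 6.

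These figures rest on assumed exponential PFS, assumed medians and assumed shares of participants held; none of these is in the documents. A systematic dose-related bias in PFS is not shown, since it needs delay rates that the documents do not give and the median can move in either direction. This is a cheap improvement to the plan and does not threaten its primary objectives.

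**What to change.** In Table 1 footnote k, footnote i of Tables 2, 3, 4 and 7, and Section 8.1.1, schedule tumor assessments at weeks 6, 12 and 18 and then every 12 weeks, counted from Cycle 1 Day 1, ±7 days, regardless of dosing delays. Delete the list of cycles, or mark it as nominal only. Every cohort then has the same scan timetable, so the delay-related difference is zero by construction; ordinary rounding to scan dates remains.

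The cost is wording in five footnotes and one section, with three practical downsides:

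- Some scans will not coincide with a dosing visit.
- With a ±7-day window, the first scan may fall after the third dose.
- Participants with delays may have slightly more scheduled scans before progression: about 1.8 rises to 2.3 for a 6-week delay at a true median of 8 weeks.
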